**Table 5: Dose Delay, Dose Reduction and Discontinuation Guidelines: (Continued)**

Event at the Day of Dosing	Action

Grade <math>\geq</math> 3 Leukopenia, neutropenia and/or thrombocytopeniai
	
Dose delayc and, repeat assessment weekly for two consecutive weeks
 
 
• Investigator should assess the cause of cytopenia per standard clinical practice to exclude hematologic malignancy.
 
• If WBC, neutrophils and platelets resolved to <math>\leq</math> Grade 1, continue with dosing at the same dose level.
 
• If WBC, neutrophils and platelets <math>\geq</math> Grade 2 and above baseline sustained for <math>\geq</math> 14 days perform bone marrow assessment. 
 
○ If hematologic malignancy is confirmed, discontinue treatmentg
 
○ If hematological malignancy is not confirmed, then discuss future dosing with a medical monitor.
 
 
 

Grade 3 Leukocytosisf
	
Discontinue treatment

a Possibly, probably or definitely related.

b Based on the **pre-treatment** Hb value not influenced by transfusion (ie,  $\geq$  14 days post- transfusion); Hb should be rechecked weekly during dose delay.

c If dose delay is 15 weeks or longer from the prior dose administration, treatment should be discontinued.

d Refer to [Table 4](#) for dose reductions.

e Central laboratory corrected WBC values must be used for confirming the Investigator decision, which may be based on the local lab result. The baseline WBC is defined as highest WBC value between Screening WBC and Study Dose 1 Day 1.

f Grade 3 Leukocytosis (as per CTCAE, ie, WBC above 100K) should be based on Central Laboratory values, as applicable.

g For full list of events triggering discontinuation, see Section 11 of the protocol.

h For reference, as per CTCAE : Grade 1 Leukopenia :  $<$  LLN – 3000/mm^3; Grade 1 Neutropenia :  $<$  LLN – 1500/mm^3; Grade 1 Thrombocytopenia :  $<$  LLN – 75'000/mm^3; Grade 2 Leukopenia :  $<$  3000 – 2000 / mm^3; Grade 2 Neutropenia :  $<$  1500 – 1000 / mm^3; Grade 2 Thrombocytopenia :  $<$  75'000 – 50'000 / mm^3.

i Grade 3 Leukopenia (as per CTCAE,  $<$  2000 - 1000/mm^3), Neutropenia (as per CTCAE, ie,  $<$  1000 - 500/mm^3) and Thrombocytopenia ( $<$  50,000 - 25,000/mm^3).

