**Table 5: Dose Delay, Dose Reduction and Discontinuation Guidelines:**

Event at the Day of Dosing	Action
Any related AE = Grade 2 a	Dose delay c until resolved to $\leq$ Grade 1 or baseline
Any related AE $\geq$ Grade 3 a	Dose delay c until resolved to $\leq$ Grade 1 or baseline, and then reduce dose by 25% d

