**Table 5: Dose Delay, Dose Reduction and Discontinuation Guidelines: (Continued)**

Event at the Day of Dosing	Action
> 2 dose reductions due to related AE a	Discontinue treatment
Increase in Hb >2.0 g/dL compared to pre-dose Hb of Day 1 of the previous treatment dose cycle b	Reduce dose by 25% d if ΔHb not influenced by RBC transfusions
Hb ≥ 11.5 g/dL b	Dose delay until Hb ≤ 11.0 g/dL
Worsening of Anemia	

A ≥ 50 % increase from baseline in transfusion burden in combination with an unexplained shift from baseline (worsening) of ≥ 2 gradesi in leukopenia, neutropenia or thrombocytopeniah.
	
Dose delayc and repeat WBC, neutrophils and platelets weekly for two consecutive weeks.
 
 
• If WBC, neutrophils and platelets are resolved to ≤ Grade 1 or baseline, continue with dosing at the same dose level.
 
• If WBC, neutrophils and platelets are Grade 2 and above baseline, then continue with dose delay until resolution to ≤ Grade 1 and evaluate for alternative explanations of cytopenia as per standard clinical practice.
 
• If shift (worsening) of ≥ 2 grades is maintained for ≥ 14 days or thrombocytopenia does not improve to < Grade 2 within 14 days and no alternative explanation is identified, then perform bone marrow assessment.                         
 
○ If hematologic malignancy is confirmed, discontinue treatmentg
 
○ If hematologic malignancy is not confirmed, then discuss future dosing with medical monitor.
 
 
 

WBC	

WBC counte ≥2X baseline in the absence of an associated condition (eg, infection or concomitant corticosteroid use)
	
Continue treatment, repeat WBC within 1 week
 
 
• If repeat WBC remains ≥ 2 X above baseline Investigator should assess the cause of increase to exclude hematologic malignancy as per standard clinical practice.
 
• If hematologic malignancy is confirmed, discontinue treatment.g
 

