### 10.3. Abnormal Laboratory Values

An abnormal laboratory value is considered to be an AE if the abnormality:

- results in discontinuation from the study;
- requires treatment, modification/ interruption of IP dose, or any other therapeutic intervention; or
- is judged to be of significant clinical importance, eg, one that indicates a new disease process and/or organ toxicity, or is an exacerbation or worsening of an existing condition.

Regardless of severity grade, only laboratory abnormalities that fulfill a seriousness criterion need to be documented as a serious adverse event.

If a laboratory abnormality is one component of a diagnosis or syndrome, then only the diagnosis or syndrome should be recorded on the AE page/screen of the eCRF. If the abnormality was not

a part of a diagnosis or syndrome, then the laboratory abnormality should be recorded as the AE. If possible, the laboratory abnormality should be recorded as a medical term and not simply as an abnormal laboratory result (eg, record thrombocytopenia rather than decreased platelets).

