## 11. DISCONTINUATIONS

### 11.1. Treatment Discontinuation

Subjects will have a treatment discontinuation visit at the time of study drug discontinuation. All subjects who received at least one dose of the study drug will be followed for 156 weeks post-treatment.

The following events are considered sufficient reasons for discontinuing a subject from the investigational product(s):

- Adverse Event(s):
  - Any serious AE assessed as related to luspatercept
  - Any AE  $\geq$  Grade 3 assessed to be related to luspatercept if the event causes a treatment delay of 15 weeks or longer from the prior administered dose, including hypersensitivity to luspatercept.
  - If a subject experiences  $> 2$  Dose Reductions due to related AE
- Any new malignancy
- Withdrawal of consent - An indication that a study participant has removed itself from the study treatment
- Death
- Lost to follow-up - the loss or lack of continuation of a subject to follow-up
- Pregnancy
- If dose is delayed for more than 15 weeks or longer from the prior dose administered dose due to AE, including case of elective surgery/hospitalization
- Other: Different than the one(s) previously specified or mentioned

The reason for discontinuation of treatment should be recorded in the eCRF and in the source documents.

The decision to discontinue a subject from treatment remains the responsibility of the treating physician, which will not be delayed or refused by the Sponsor. However, prior to discontinuing a subject, the Investigator may contact the Medical Monitor and forward appropriate supporting documents for review and discussion.

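### Table 5 gives two incompatible next doses for a related Grade ≥3 cytopenia that recovers to Grade 1 or below, and does not say which row governs

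*Protocol*

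**What the plan says.** Four parts of the protocol bear on the same event.

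- **Table 5, related adverse events of Grade ≥3.** Dosing is delayed until the event is at or below "Grade 1 or baseline, and then reduce dose by 25" percent. Table 4 gives the dose levels. Footnote a defines related to include possibly related.
- **Table 5, Grade ≥3 "Leukopenia, neutropenia and/or thrombocytopenia".** Dosing is delayed with weekly repeat counts. If counts have come down to at or below "Grade 1, continue with dosing at the same dose level". A cytopenia that stays at Grade 2 or worse and above baseline for 14 days or more goes to bone marrow assessment instead.
- **Table 5, Worsening of Anemia.** This row also resumes at the same dose on recovery ("Grade 1 or baseline, continue with dosing at the same dose level"). It applies only when transfusion burden has risen by at least 50% "in combination with an unexplained shift from baseline (worsening) of" two or more grades in one of these cell lines.
- **Stopping rule.** Treatment ends after more than "2 dose reductions due to related AE". Section 11.1 repeats the rule with the words "Dose Reductions due to related AE".

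Section 10.3 classes a laboratory abnormality as an adverse event if, among other triggers, it "requires treatment, modification/ interruption of IP dose, or any other therapeutic intervention".

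**The concern.** A Grade ≥3 cytopenia on a dosing day requires a delay, so Section 10.3 makes it an adverse event. If the investigator also judges it related, the site has two instructions for the dose after recovery: reduce it, or leave it unchanged. Both cannot be followed. Two sites acting in good faith could give different doses to similar subjects.

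The reading also matters beyond the next dose. Only reductions actually made count toward the stop for more than two, so one reading moves a subject toward discontinuation and the other does not. SAP Section 11.1 tabulates treatment-emergent events leading to dose reduction and to discontinuation, and SAP Section 9.4 summarises dose reductions and their reasons. Those counts would partly reflect how a site read Table 5.

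**Working it through.** The plan states no figure to reproduce. The check compares the texts and then traces the doses in Table 4.

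**Do the two rows cover the same event?**

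1. The cytopenia row is defined by cell line and grade. It is not limited to unrelated events.
2. The related-event row covers any related adverse event of Grade ≥3. It does not exclude laboratory events or cytopenias.
3. Section 10.3 makes a cytopenia that delays dosing an adverse event.
4. A Grade ≥3 cytopenia judged related therefore meets both rows on the same day. The rows agree on the delay. They differ on the dose once counts reach Grade 1 or below.

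**Is precedence stated anywhere?** Table 5 and its footnotes, Sections 7.2, 7.2.1.2 and 11.1, and SAP Section 9.4 contain no such statement. Section 7.2.1.2 refers to Table 5 for reductions due to related events and makes no exception for cytopenias.

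**Does the Worsening of Anemia row conflict as well?** Only in part. A shift from Grade 0 to Grade 2 can satisfy that row, and a related Grade 2 event is delayed without a reduction, so the dose actions agree. They conflict only when the row's own conditions hold and the event is also a related adverse event of Grade ≥3. A reader may further hold that an event attributed to the study drug is not an unexplained shift.

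**Size of the dose difference.** The Table 4 levels are 1.25, 1.0, 0.8, 0.6 and 0.45 mg/kg.

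- First reduction from 1.0: (1.0 − 0.8)/1.0 = 20%. The table's label is approximately 25%.
- Second reduction: (0.8 − 0.6)/0.8 = 25%.

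The trace below is an illustration only. It assumes a subject starting at 1.0 mg/kg, with every event related and each recovering to Grade 1 or below.

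| After event | Related-event row | Cytopenia row | Ratio of doses |
|---|---|---|---|
| 1 | 0.8 mg/kg, 1 reduction | 1.0 mg/kg, 0 reductions | 1.0/0.8 = 1.25 |
| 2 | 0.6 mg/kg, 2 reductions | 1.0 mg/kg, 0 reductions | 1.0/0.6 = 1.67 |
| 3 | third reduction exceeds 2: stop | 1.0 mg/kg, 0 reductions | not applicable |

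**The case against.** **The specific row overrides the general one.** This is the strongest reply. The related-event row is a catch-all, while the cytopenia row is a dedicated algorithm that was added later. Many readers would apply the dedicated row, but the protocol never says so. The amendment justification describes the new criteria as additional, not as replacing the existing ones. Section 7.2 also lists related events below Grade 2 and cytopenias below Grade 3 as separate conditions for dosing, both of which must hold. A Grade 2 neutropenia recorded as a related event passes the second and fails the first, so the general rule is not switched off for cytopenias.

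**Other safeguards remain.** This stands. A reader might infer that repeated cytopenias could never end treatment under the same-dose reading. The documents do not support that. A delay of 15 weeks or longer, a related serious adverse event and a confirmed hematologic malignancy all still lead to discontinuation, and a sustained cytopenia goes to marrow assessment. Only the stop based on the number of reductions is bypassed.

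**The sponsor sees dose changes.** Section 7.2.1.2 requires notification of a modification or interruption within 24 hours, and reductions are registered in the IRT. This may limit divergence in practice, but the sponsor has no written rule to apply either.

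**The primary results are untouched.** This also stands. The cytopenia rows came in with the amendment that followed Amendment 1. SAP Section 2 lists amendment versions of 21 April 2017 and 11 December 2018, so the later date is inferred for these rows. The primary report used data to 11 May 2018, and SAP Sections 10.2 and 10.3 plan no further primary or key secondary analysis. A reader might extend the point to the primary endpoint; nothing here supports that.

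**Conclusion.** The point holds in a limited form. For a Grade ≥3 leukopenia, neutropenia or thrombocytopenia that is judged related and recovers to Grade 1 or below, Table 5 contains two incompatible dose actions and no rule for choosing between them. This is a contradiction within a dosing and stopping rule, not a missing detail. The Worsening of Anemia row shares it only where its extra conditions are met and the event is also a related adverse event of Grade ≥3.

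The consequence is one Table 4 step per event, 20% for the first step from 1.0 mg/kg, together with a difference in the reduction count used for stopping. After two such events the illustrated doses are 0.6 and 1.0 mg/kg. How often this would occur cannot be judged, because the documents give no frequency for related Grade ≥3 cytopenia or its recurrence. The effect on analysis is confined to the dose-modification summaries and the tables of events leading to reduction or discontinuation. It merits correction because it concerns subject safety and is easily resolved.

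**What to change.** The sponsor should reconcile the related-event row and the Grade ≥3 cytopenia row, and the Worsening of Anemia row where it overlaps. Table 5 should state:

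1. which dose action governs when a Grade ≥3 cytopenia is assessed as related and has recovered; and
2. whether such an event counts toward the stop for more than two reductions due to related events.

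Section 11.1 should carry the same statement on counting. The choice of dose action is a clinical one for the sponsor, and no view is given on it here.

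The cost is a sentence or footnote in Table 5, a matching line in Section 11.1 and a memo to sites. No additional data are needed.

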### 7.2.1.3. Overdose

Overdose, as defined for this protocol, refers to luspatercept dosing only. On a per dose basis, an overdose is defined as the following amount over the protocol-specified dose of luspatercept assigned to a given subject, regardless of any associated adverse events or sequelae.

SC 10% over the protocol-specified dose

On a schedule or frequency basis, an overdose is defined as anything more frequent than the protocol required schedule or frequency. Complete data about drug administration, including any overdose, regardless of whether the overdose was accidental or intentional, should be reported in the eCRF. See Section 10.1 for the reporting of adverse events associated with overdose.

### 7.3. Method of Treatment Assignment

The treatment assignment (randomization) will occur at the end of the Screening Period, once all the required screening procedures have been completed and all required data have been submitted to the Sponsor or its authorized representative. Upon receiving acknowledgment of subjects' eligibility from the Sponsor or its authorized representative, subject can be assigned for treatment using IRT. This study will utilize the IRT for enrollment.

Designated research personnel at each investigational site will be assigned password protected, coded identification numbers which gives them the authorization to call into IRT to enroll subjects. For drug assignment at each dose start and in the event of any dose reduction, dose titration site staff must contact IRT to record the new dose level and obtain the new study treatment assignment.

The relationship of the randomization number to the subject ID number will be described by a randomization algorithm. The randomization algorithm will be employed by the IRT system to assign a subject to a treatment based on the prespecified rules, such as double blind study, stratified randomization with randomization ratio active vs placebo on a 2:1; subjects will be placed into the appropriate stratum per the responses/data entered/collected for questions collecting stratification and based on the combination of these data points, the IRT will place the subject in the next available slot within the appropriate stratum for that subject. The IRT will be utilized to ensure an equal weight central randomization based on randomization method according to stratification factor defined in Section 3.1, Study Design. The randomization number corresponds to a particular treatment arm within a stratum. The randomization number, by itself, will not unblind a user to the subject's treatment. The randomization number should be coupled with all the unblinded code information, in order the subject to become unblinded.

### 7.4. Packaging and Labeling

The label(s) for luspatercept will include Sponsor name, address and telephone number, the protocol number, IP name, dosage form and strength (where applicable), amount of IP per container, lot number, expiry date (where applicable), medication identification/kit number, dosing instructions, storage conditions, and required caution statements and/or regulatory statements as applicable. Additional information may be included on the label as applicable per local regulations.

#### 7.4.1. Blinding

For this trial, all subjects, study site staff and Celgene Corporation representatives with the exception of designated individuals (eg, the pharmacist at the investigational site), will remain blinded to all treatment assignments until all subjects completed 48 weeks of double-blind treatment or discontinue before reaching 48 weeks double-blind treatment, whichever is the earlier date, or at the time the study is unblinded (per DMC recommendation) and the data base is locked.

The designated site individual (for example the pharmacist) at the investigational site will use a syringe (that exactly matches the syringe used for reconstituted luspatercept) and sterile normal saline (0.9% sodium chloride for injection) to prepare a matching placebo. Thus, the designated

site individual at the Investigational site will be unblinded and will give Investigators and their staff luspatercept and placebo in a blinded manner.

Randomization, drug dispensing, dose reduction/titration, and drug discontinuation will be accomplished by an IRT system. Authorized site personnel must contact the IRT for randomization, study drug assignment at the beginning of each cycle, to register dose reductions or titrations, and treatment discontinuation. Confirmation of each call will be sent to the investigational site and Celgene.

For emergency unblinding refer to Section 12.2.

## 7.5. Investigational Product Accountability and Disposal

Accountability for study drug that is administered during the course of the study is the responsibility of the Investigator or designee. Investigational clinical supplies must be received by a designated person at the clinical site and kept in a secure and temperature-controlled location. The investigational site must maintain accurate records demonstrating dates and amounts of study drug received, to whom it was administered (subject-by-subject accounting), and accounts of any luspatercept accidentally or deliberately destroyed or returned. Accurate recording of all IP administration will be made in the appropriate section of the subject's eCRF and source documents. Unless otherwise notified, all vials of study drug, both used and unused, must be saved for drug accountability. The used vials may be discarded, per the institution's standard practice, after drug accountability has been completed by the monitor. The Investigator must return all unused vials of study drug to the Sponsor at the end of the study, or the study drug may be destroyed at the clinical site with the permission of the Sponsor. For either scenario, the outcome must be documented on the drug accountability log. The Sponsor will provide direction for the outcome of all unused vials.

Celgene (or designee) will review with the Investigator and relevant site personnel the process for investigational product return, disposal, and/or destruction including responsibilities for the site versus Celgene (or designee).

## 7.6. Investigational Product Compliance

Study drug will be administered as a SC injection at the clinical site by the study staff. Monitoring for subject compliance with the treatment regimen is therefore unnecessary.

Accurate recording of all IP administration will be made in the appropriate section of the subject's eCRF and source documents.

The Investigator or designee is responsible for accounting for all IP that is administered during the course of the study.

## 8. CONCOMITANT MEDICATIONS AND PROCEDURES

During screening and throughout the study subjects may take stable doses of medications for chronic conditions that are not specifically excluded by the protocol (see Sections 4.2 Inclusion Criteria and 4.3 Exclusion Criteria). The Investigator should consult the medical monitor regarding any questions about whether a new medication or dosage of existing medication would require the patient to discontinue from the study.

Prior/Concomitant medications will be collected beginning at study Screening/Run-in Period and will include all medications taken within 12 weeks prior to Dose 1 Day 1.

For information regarding other drugs that may interact with IP and affect its metabolism, pharmacokinetics, or excretion, please see the Investigators Brochure and/or local package insert.

### 8.1. Permitted Concomitant Medications and Procedures

#### 8.1.1. General Concomitant Medication Usage

During screening and throughout the study subjects may take stable doses of medications for chronic conditions that are not specifically excluded by the protocol (see Section 4.3 Exclusion Criteria).

The Investigator should consult the medical monitor regarding any questions about whether a new medication or dosage of existing medication would require the patient to discontinue from the study.

All concomitant treatments, used from 12 weeks prior to first dose of IP until the End of Study visit must be reported on the eCRF.

All prior and concomitant blood and blood products received, iron chelating and antihypertensive therapies used from 24 weeks prior to first dose of IP until the End of Study visit must be reported on the eCRF.

#### 8.1.2. Concomitant Medication for Anemia

Concurrent therapy with a new prescription medication related to the treatment of anemia during the course of the study must first be discussed with the Medical Monitor prior to administration, unless appropriate medical care necessitates that the medication should begin before the Medical Monitor can be consulted.

If treatment with hydroxyurea is required during the treatment period, the patient should be discontinued from treatment with study drug and enter the follow-up period.

